***Recruitment***

Recruiting will be undertaken in the diabetes clinics at Imperial College Healthcare NHS Trust, from registered research databases and from interested subjects who contact us. Participant information sheets will be given to potential subjects and, after a minimum of 48 hours and following any questions, informed consent will be taken.

Subjects who have already participated in phase 1 and/or 2 of the study can also be recruited for phase 4 and they will be re-screened and re-consented.

**Visit 1: Screening**

- Attend the clinical research unit
- Routine clinical examination
- ECG
- Non-fasting venous blood taken for HbA1c, creatinine, lipids.
- Urine for albumin/creatinine ratio
- Urine pregnancy test in female subjects of childbearing age
- CHO counting and hypoglycaemia education revision by a qualified health care professional.
- The basal insulin dose, insulin:carbohydrate ratio (ICR) and insulin sensitivity factor (ISF) will be reviewed and adjusted if needed.
- PAID score, DQOL and DTSQ questionnaire to be completed
- Real-time continuous glucose monitor (Dexcom) placed in the anterior abdominal wall according to manufacturer's instructions.
- Subjects will be shown how to insert the sensor themselves, interpret the CGM data in real time and to set the hypo- and hyperglycaemia threshold alarms. The alarm threshold will be set at 4mmol/l and 11mmol/l and subjects will be encouraged to keep it at those levels and not to reduce the hypoglycaemia threshold below 3.3mmol/L.
- Subjects to complete a 4-week run-in period using RT-CGM (Dexcom) to familiarize themselves with the RT-CGM and for optimization of treatment prior to study start
- Instructions to subjects to ensure:

- Capillary blood glucose measurements fasting, pre-meals and pre-bed.
- Calibration of the CGM every 12 hours and sensor change every 7 days as per manufacturer's instructions (a copy will be given to subjects)
- Food diaries and physical activity record to be kept for the 4-week run-in period

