**Visit 1: Screening**

- Attend the clinical research unit
- Routine clinical examination
- ECG
- Non-fasting venous blood taken for HbA1c, creatinine, lipids.
- Urine for albumin/creatinine ratio
- Urine pregnancy test in female subjects of childbearing age
- CHO counting and hypoglycaemia education revision by a qualified health care professional.
- The basal insulin dose will be reviewed and adjusted if needed.
- Questionnaires to be completed
- Continuous glucose monitor (CGM retrospective/blinded iPro2, Medtronic or Dexcom) placed in the anterior abdominal wall according to manufacturer's instructions. CGM sensor to be worn for 6-7 continuous days.
- Instructions to subjects to ensure:
  - Capillary blood glucose measurements fasting, pre-meals, post-meals and pre-bed.
  - Food diaries and physical activity record to be kept for 6 days

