#### **Visits 3-6: Weekly CGM and update of CBR algorithm**

- Attend clinical research unit on day 7 following visit 2 and then day 14, 21 and 28.
- Upload data from the smartphone ABC4D application to the desktop PC and store it in the corresponding folder.
- Remove CGM, upload data to Medtronic Carelink Pro software or DiaSend/Dexcom Studio. The CGM data will not be disclosed to the subject.
- Export uploaded CGM data to a text file (i.e. csv) and store it in the corresponding folder.
- Using the ABC4D PC application, update the CBR algorithm case base with the uploaded data from the CGM and the data from ABC4D smartphone application. The algorithm update with new cases will be an automatic process without the research team approving each case.
- New CGM (blinded iPro2, Medtronic or Dexcom) placed in the anterior abdominal wall according to manufacturer's instructions.

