### **Visits 3-8: CGM at 1, 3 and 6 months**

*Visits 3, 5, and 7:*

- Attend clinical research unit at start of week 4, 12 and 24 of the study
- New CGM (retrospective/blinded iPro2, Medtronic or Dexcom) placed in the anterior abdominal wall according to manufacturer's instructions.

*Visits 4, 6 and 8:*

- Attend clinical research unit at end of week 4 (7 days after insertion of CGM), 12 and 24 of the study.
- Remove CGM, upload data to Medtronic Carelink Pro software or DiaSend/Dexcom Studio. The CGM data will not be disclosed to the subject.

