**Secondary outcomes:**

HbA1c at 3 months  
Post-prandial AUC at 4 hours and 6 hours  
Post-prandial AUC (<3.9) at 4 hours and 6 hours  
Episodes of hypoglycaemia within 4- and 6-hours post-prandially  
% time in target glucose (3.9-10mmol/l)  
% time in hypo- (<3.9mmol/l) and hyperglycaemia (>10mmol/l)  
Glycaemic risk: LBGI and HBGI  
Glycaemic variability: MAGE and CONGA-2  
Change in weight (kg)  
Number achieving target HbA1c (≤ 53 mmol/mol)  
24-hours insulin dose requirements  
PAID score questionnaire  
DQOL questionnaire  
DTSQ Questionnaire  
Acceptability questionnaire (non-validated)

These are validated, published metrics.

**Timescale:** Each subject will be in the study for 6 months. It is anticipated that it will take 15 months to complete the 4th phase.

**Population:** 142 subjects with T1DM, are required to demonstrate an HbA1c difference of 0.6% with  $\alpha$  of 0.05 and 90% power (two-tailed). We aim to screen n=180 and randomise n=90 in each group. This power calculation is based on using a population mean HbA1c of 7.9% with a standard deviation of 1.1.

The first 25 participants will be randomised to either the ABC4D running in semi-automatic mode (where the revisions are done using a semi-automatic process-see page 23) or a standard bolus calculator. The remaining participants will be randomised to either the fully automated ABC4D (where revisions are fully automated) or a standard bolus calculator. Screening 180 participants will ensure that at least 142 participants are included to enable demonstration of a significant difference between the fully automated ABC4D system and a standard bolus calculator.

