### **Intervention group:**

Intervention: ABC4D with RT-CGM for 6 months

Visit 2: CGM review and intervention study start

- Attend 4 weeks after visit 1
- Remove CGM, upload data to DiaSend/Dexcom Studio software (subject can do upload the data at home prior to attending the visit) and review data with subject.
- Adjust ICR, ISF and basal rates if deemed necessary based on CGM data.
- Initialize CBR algorithm case base with 3 standard cases (breakfast, lunch and dinner) using subjects existing ICR
- Switch on the ABC4D device
- Instructions to subjects to ensure:
  - Capillary blood glucose measurements fasting, pre-meals and pre-bed.
  - Accurate subject input of pre-meal capillary blood glucose, carbohydrate (CHO) amount (g), alcohol (none/<2units/>2units), pre- or post-meal exercise (none/moderate/intense), type of meal absorption (fast/medium/slow), illness (yes/no), stress (none/mild/severe), menstrual cycle and insulin given if CBR algorithm advice not taken
  - Calibration of the CGM every 12 hours and sensor change every 7 days as per manufacturer's instructions
  - No correction boluses for 2 hours post-meal unless clinically indicated (CBG >15mM or ketosis)
- A detailed ABC4D user guide will be given to the subject

Follow-up clinic visits at 1 month, 3 months and 6 months:

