### Visit 2: CGM review and control study start

- Attend 4 weeks after visit 1
- Remove CGM, upload data to DiaSend/Dexcom Studio software (subject can do upload the data at home prior to attending the visit) and review data with subject.
- Adjust ICR, ISF and basal rates if deemed necessary based on CGM data.

Follow-up clinic visits at 1 month, 3 months and 6 months:

### Visit 3

Review at 1 month:

- Review of subject's diabetes control including insulin requirements, incidence of hypoglycaemia, exercise, driving etc.

### Visit 4

Review at 3 months:

- Review of subject's diabetes control including insulin requirements, incidence of hypoglycaemia, exercise, driving etc.
- Random venous blood taken for HbA1c
- Weight (kg)

### Visit 5

Review at 6 months:

- Review of subject's diabetes control including insulin requirements, incidence of hypoglycaemia, exercise, driving etc.
- Random venous blood taken for HbA1c
- Weight (kg)
- PAID score questionnaire and acceptability questionnaire to be completed

Usual care will be maintained for diabetes throughout the study. No concomitant medical therapies are contra-indicated, except GLP-1 analogues, SLGT2 inhibitors and gliptins. Support will be offered to any participants who have concerns about their diabetes management.

Subjects in the intervention group using the ABC4D will have the opportunity to call a physician for medical support and an engineer for technical support 24 hours a day throughout the study.

*Statistics* This is a randomised study with an intervention group and a control group. Outcomes from the study are absolutes as described above. 142 subjects with T1DM, are required to demonstrate an HbA1c difference of 0.6% with  $\alpha$  of 0.05 and 90% power (two-tailed). We aim to screen n=160 and randomise n=80 in each group. This power calculation is based on using a population mean HbA1c of 7.9% with a standard deviation of 1.1.

The sample size is comparable to other technology transfer studies, is a realistic number for recruitment and provides robust clinical validation and safety date of a new technology.

[figure not shown]
Missing, unused, and spurious data will be assessed on an individual basis and may be ignored, withdrawn or the visit may be removed from the analysis with appropriate justification adjudicated by the Principal Investigator.

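### Phases 3 and 4 schedule no collection of control-arm meal times after baseline, so the post-prandial secondary outcomes have no common basis in the two arms

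*Combined protocol and SAP*

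**What the plan says.** **Outcomes.** The secondary outcome lists of Phases 3 and 4 contain the same 15 lines. Three are tied to meals: "Post-prandial AUC at 4 hours and 6 hours", the corresponding AUC below 3.9, and "Episodes of hypoglycaemia within 4- and 6-hours post-prandially".

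**Meal records before the comparison starts (both arms).** Phase 3, Visit 1: "Food diaries and physical activity record to be kept for 6 days". Phase 4, Visit 1: "Food diaries and physical activity record to be kept for the 4-week run-in period".

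**Meal records afterwards, ABC4D arm.** At Visit 2 of both phases participants are told to enter their meal data in the app. The Phase 4 instruction begins "Accurate subject input of pre-meal capillary blood glucose, carbohydrate (CHO) amount (g), alcohol (none/<2units/>2units), pre- or post-meal exercise (none/moderate/intense" and continues with meal absorption type, illness, stress and other items. Phase 3 then schedules, at Visits 3-6 and again at Visits 8, 10, 12, 14 and 16: "Upload data from the smartphone ABC4D application to the desktop PC and store it in the corresponding folder". In Phase 4 the section on case base revision has the case base revised every two weeks without a clinic visit.

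**Control arm afterwards.** In Phase 3, at the end of weeks 4, 12 and 24, the list reads "Remove CGM, upload data to Medtronic Carelink Pro software or DiaSend/Dexcom Studio". In Phase 4, Visit 2 has "Remove CGM, upload data to DiaSend/Dexcom Studio software". Visits 3 to 5 then list a clinical review, HbA1c and weight at 3 and 6 months, and questionnaires at 6 months. No control list in either phase names a diary after baseline or a download from a pump, meter or app.

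**Control devices.** Under Randomisation, standard care is a pump bolus wizard, a bolus calculator in a glucose meter, or the ABC4D app without CBR adaptation.

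**The concern.** A post-prandial AUC or hypoglycaemia count starts from a meal. Without a recorded start time there is no 4-hour or 6-hour window to integrate over. With start times obtained differently in each arm, the two sets of windows do not cover the same kind of meal.

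In the ABC4D arm the analysed meals would be those entered in the app. In controls they would have to come from whatever could be recovered later. For example, if control meals were inferred from rises in the CGM trace, meals with a small excursion would tend to be missed. The control AUC would then be raised by the method of detection alone.

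These outcomes lie closest to what a bolus calculator is meant to change. The trial is open label, and meal start is not defined anywhere in the plan. The only rule for gaps is case-by-case adjudication by the Principal Investigator, which does not protect against a gap that differs by arm. Meal times that are not retrieved prospectively may not be recoverable.

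**Working it through.** No figure in the plan is in dispute here. The primary sample size reproduces: n per arm = 2 × (1.960 + 1.282)² × 1.1² / 0.6² = 70.6, rounded up to 71, or 142 in total. The point changes nothing in it.

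**1. What is affected.** There are 15 secondary lines and 3 need meal times. Each has a 4-hour and a 6-hour version, so 3 × 2 = 6 measures.

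**2. What each measure needs.** It needs (a) a meal start time and (b) a CGM trace over the following 4 or 6 hours, both retrieved for analysis.

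**3. The lists side by side, after baseline.**

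| | Meal time recorded | Meal record retrieved | CGM retrieved |
|---|---|---|---|
| Phase 3, ABC4D | Instructed, in app | Scheduled at Visits 3-6, 8, 10, 12, 14, 16 | Scheduled at the same visits |
| Phase 3, control | Not instructed; depends on device | Not scheduled | Scheduled, end of weeks 4, 12, 24 |
| Phase 4, ABC4D | Instructed, in app | Not in the Visit 3-5 lists; implied by case-base revision | Not in the Visit 3-5 lists; implied by case-base revision |
| Phase 4, control | Not instructed; depends on device | Not scheduled | Not scheduled after Visit 2 |

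The meal-time gap is in the control arm of both phases. The CGM gap is in Phase 4 only. There, the visit lists of both arms are silent, but only the ABC4D arm has another process that implies continuing transfer. (The Phase 4 text gives the revision interval as two weeks and the overview table gives one week; either implies transfer.)

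**4. Common windows in Phase 3.** ABC4D sensors cover weeks 1-4, 8, 12, 16, 20 and 24: 4 + 5 = 9 weeks. Control sensors cover weeks 4, 12 and 24: 3 weeks. The overlap is weeks 4, 12 and 24. The plan does not say that the comparison is confined to these weeks.

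**5. Reach of the Phase 4 CGM gap.** Besides the 3 post-prandial lines, CGM data underlie time in target, time in hypo- and hyperglycaemia, LBGI/HBGI, and MAGE/CONGA-2. That is 3 + 4 = 7 of 15 lines.

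**6. What cannot be computed.** The documents do not say how many controls will use each device type, or whether the pumps and meters keep time-stamped carbohydrate or bolus entries. Neither the share of controls with recoverable meal times nor the size of any bias can be derived.

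**The case against.** The strongest reply is that the data will probably exist. Every control option is a bolus calculator, and the Background lists meal carbohydrate among a standard calculator's inputs. The ABC4D app logs meal events and controls may use it. In Phase 4 both arms wear RT-CGM throughout, the section on glucose sensors says that Dexcom data will be downloaded, and participants may upload from home before Visit 2. The visit lists are not exhaustive either: for the Phase 4 ABC4D arm the text has questionnaires at Visit 5, while the overview table marks them at Visit 1 only. An omission from a list may be an editing gap.

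Much of this stands, and it rules out several stronger conclusions that a reader might draw:

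- *That controls have no source of meal times, so the comparison is impossible.* A source may exist. What is missing is its scheduled retrieval and a definition of meal start.
- *That Phase 4 control CGM will never be downloaded.* The general statement on Dexcom data is not limited to one arm. It gives no schedule, and the ABC4D Visit 3 to 5 lists are equally silent.
- *That all controls are affected over the full 24 weeks.* In Phase 3, control CGM covers three scheduled weeks and is downloaded. In either phase, controls using the app would have logged meals.
- *That 24-hour insulin dose has the same defect.* It needs no meal time, and the clinical reviews cover insulin requirements in the same words in both arms.

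What the reply does not meet is the asymmetry. A log that may sit on a device is not collected data. Even complete control CGM would leave meal start undefined in that arm.

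**Conclusion.** The point holds as a gap in data collection that differs by arm. As written, Phases 3 and 4 give the ABC4D arm a meal log, with upload scheduled in Phase 3 and implied in Phase 4. They schedule no retrieval of meal or bolus records for controls after baseline. Six post-prandial measures (3 of 15 secondary lines) would therefore be missing in controls or ascertained differently. The control arm is planned at 80 in Phase 3, and in Phase 4 at 90 (Population) or 80 (Statistics); how many of these participants would lack usable meal times is unknown. In Phase 4, all seven CGM-based secondary lines in controls also depend on a download that has no schedule.

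This rests on two assumptions: that sites collect what the visit lists and general sections say and no more, and that no separate data-collection manual fills the gap. If such a manual exists, the remedy shrinks to citing it and defining meal start.

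The primary outcome is venous HbA1c, taken in both arms, and it is untouched, as is the sample size. The point should be settled while meal times can still be collected, but it does not threaten the main conclusion of either phase.

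**What to change.** 1. At control visits that already exist (Phase 3 Visits 4, 6 and 8; Phase 4 Visits 3, 4 and 5), schedule a download of the bolus-calculator log, whether pump, meter or app. In Phase 4 add the CGM download at the same visits, and write the corresponding CGM and app transfer into the ABC4D visit list.
2. Define meal start by one rule in both arms: the time-stamped carbohydrate or meal-bolus entry.
3. Name common analysis windows. In Phase 3 these are the CGM weeks ending at weeks 4, 12 and 24. In Phase 4, where wear is continuous, state the same windows for both arms.
4. Where a control device stores no time-stamped entries, ask for a brief meal-time record during those windows. Failing that, label the between-arm post-prandial comparison descriptive and rely on CGM measures that need no meal times. This fallback presupposes that the Phase 4 control CGM data are downloaded under step 1.

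The cost is a few minutes of download and some extra data handling per visit, plus a paragraph in the analysis plan. Moving controls onto the ABC4D app, or reporting the outcomes for one arm only, would be a larger change than the gap requires.

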### ***Randomisation***

Subjects who fit the inclusion criteria will be randomized to either ABC4D (intervention group) or standard care (control group) in a 1:1 ratio. Both groups will be using RT-CGM.

Standard care is defined as the bolus wizard within insulin pumps, bolus calculator in glucose meter or the ABC4D app as a standard bolus calculator (without CBR adaptation).

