#### **Visit 2: CGM review and ABC4D start**

- Attend 7 days following visit 1
- Remove CGM, upload data to Medtronic Carelink Pro software or DiaSend/Dexcom Studio, enter and review data with subject.
- Recalculate ISF and ICR after CGM and review of different types of carbohydrates.
- Initialize CBR algorithm case base with cases derived from the CGM data and diary.
- Switch on the ABC4D device
- Instructions to subjects to ensure:
  - Capillary blood glucose measurements fasting, pre-meals, post-meals and pre-bed.
  - Accurate subject input of pre-meal capillary blood glucose, pre- or post-meal exercise (moderate or intense), type of meal absorption (fast, medium, slow), carbohydrate (CHO) amount (g) and insulin given if CBR algorithm advice not taken
  - No correction boluses for 2 hours post-meal unless clinically indicated (CBG  $>15\text{mM}$  or ketosis)
- A detailed ABC4D user guide will be given to the subject
- CGM (blinded iPro2, Medtronic or Dexcom) placed in the anterior abdominal wall according to manufacturer's instructions.

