### Phase 3 of ABC4D study: Overview of study

### Phase 4

**Objective:** To demonstrate efficacy of the ABC4D with real-time CGM (RT-CGM) compared to standard care with RT-CGM

Standard care is defined as the bolus wizard within insulin pumps, bolus calculator in glucose meter or the ABC4D app as a standard bolus calculator (i.e no CBR adaptation).

**Methodology** Randomised open-label study

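### In open-label Phase 4, the written order puts a discretionary adjustment of insulin settings after randomisation, so it can be made with the allocation known

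*Combined protocol and SAP*

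**What the plan says.** **Phase 4.** The methodology is given as "Randomised open-label study". At Visit 1 (Screening), "The basal insulin dose, insulin:carbohydrate ratio (ICR) and insulin sensitivity factor (ISF) will be reviewed and adjusted if needed". The same section sets a run-in: "Subjects to complete a 4-week run-in period using RT-CGM (Dexcom"), partly "for optimization of treatment prior to study start". The Randomisation section follows: "Subjects who fit the inclusion criteria will be randomized to either ABC4D (intervention group) or standard care (control group"), with 1:1 allocation. It names no visit or day. Visit 2, four weeks after Visit 1, is then set out once under the intervention group and once under the control group. Both versions contain the CGM review and the same instruction: "Adjust ICR, ISF and basal rates if deemed necessary based on CGM data". In the intervention arm, the ABC4D case base is initialised at this visit from the participant's existing ICR.

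**Phase 3.** This phase is also randomised and open-label, and its Randomisation section likewise stands between Visit 1 and an arm-specific Visit 2. The instruction differs, however. In both arms it reads "Recalculate ISF and ICR after CGM and review of different types of carbohydrates", with no discretionary qualifier and no basal adjustment. Basal insulin is reviewed at Visit 1.

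The primary outcome in both phases is HbA1c at 6 months. For neither phase does the text state when the allocation is disclosed, how it is concealed, how settings are to be adjusted, or whether the person adjusting them is blinded.

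**The concern.** A visit that exists in two arm-specific versions presupposes that the arm is known. If staff follow the Phase 4 text in order, they decide whether and how far to adjust ICR, ISF and basal rates knowing which calculator the participant will use.

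These settings feed directly into treatment. The Background section lists the insulin-to-carbohydrate ratio and the sensitivity factor among the inputs of a standard bolus calculator. The control calculator has no case-based adaptation, so it does not correct a poor starting value by itself. ABC4D starts from the existing ICR but is revised during the study. Less thorough tuning in the control arm could therefore look like a benefit of ABC4D, and more thorough tuning there could hide one. Measuring HbA1c in a laboratory does not protect against this, because the treatment itself would differ between arms.

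**Working it through.** **1. Order of steps as written**

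| Step | Phase 4 | Phase 3 |
|---|---|---|
| Visit 1 | Basal dose, ICR and ISF reviewed; run-in for optimisation; screening HbA1c | Basal dose reviewed; screening HbA1c |
| Next section | Randomisation, 1:1, no date | Randomisation, 1:1, no date |
| Visit 2, each arm | ICR, ISF and basal rates adjusted at discretion | ISF and ICR recalculated for everyone |
| Visit 2, intervention arm only | Case base seeded from existing ICR, ABC4D started | Case base seeded from CGM data and diary, ABC4D started |

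In both phases some setting of insulin parameters follows the Randomisation section. It is discretionary only in Phase 4. The screening HbA1c precedes that section in both phases, so the baseline value is unaffected.

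**2. The plan's sample size**

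Inputs from the Phase 4 Population section: difference 0.6%, SD 1.1, two-sided alpha 0.05, power 90%, 1:1.

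n per arm = 2 × SD² × (1.960 + 1.282)² / difference² = 2 × 1.21 × 10.51 / 0.36 = 70.6, rounded up to 71. The total is 142, as stated. Moving the time of randomisation changes none of these inputs.

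**3. What a shift would do (illustration only)**

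The documents give no size for any bias, so the shift b in the between-arm HbA1c difference is an assumption. With m per arm:

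- SE = 1.1 × √(2/m). For m = 71 this is 0.185.
- Type I error with no true effect = 1 − Φ(1.96 − b/SE) + Φ(−1.96 − b/SE).
- Power when the shift works against a true 0.6% effect is the power for a difference of 0.6 − b.

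Phase 4 gives two randomisation targets, 90 per group (Population) and 80 per group (Statistics). These need reconciling as a separate matter. Each cell shows type I error / power.

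| Assumed b | 71 per arm | 80 per arm | 90 per arm |
|---|---|---|---|
| 0 | 5% / 90.1% | 5% / 93.2% | 5% / 95.5% |
| 0.1% | 8.4% / 77.3% | 8.9% / 82.0% | 9.4% / 86.2% |
| 0.2% | 19.2% / 58.2% | 21.0% / 63.3% | 23.0% / 68.4% |
| 0.3% | 36.9% / 36.9% | 40.7% / 40.7% | 44.8% / 44.8% |

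**4. How such a shift might arise (assumed)**

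If a fraction of one arm received extra tuning worth 0.3% HbA1c each, the mean shift would be that fraction times 0.3:

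- 20% of the arm: 0.20 × 0.3 = 0.06%, which is 0.06/0.6 = 10% of the target difference. Type I error at 71 per arm is about 6%.
- 40% of the arm: 0.40 × 0.3 = 0.12%, which is 20% of the target. Type I error is about 10%.

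On this assumption b = 0.3% would require the whole of one arm to be tuned differently, so the last row of the table is an extreme.

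**The case against.** The strongest reply is that the order is inferred from layout. Neither Randomisation section names a visit, and setting out Visit 2 once per arm is a common way to present a two-arm schedule. Randomising late in Visit 2, after the CGM review, is not ruled out. The overview figures for these phases were not available in the text examined and might show the timing. This stands, and it limits the point to what happens if the text is followed as ordered. It does not remove the point, because staff could follow the protocol either way.

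The adjustment wording is also identical in both arms and tied to CGM data. This stands too: nothing in the documents shows differential handling.

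Four stronger readings are tempting, and the documents do not support them:

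- **That all optimisation is done with the arm known.** Phase 4 reviews the settings at Visit 1 and uses the run-in for optimisation, both described before the Randomisation section. Visit 2 is a further adjustment.
- **That Phase 3 has the same discretion.** It recalculates ISF and ICR for everyone and lists no basal adjustment at Visit 2. The method is not given, so some latitude remains.
- **That people who leave the Phase 4 run-in become post-randomisation losses.** Run-in completion is not among the inclusion criteria, but the run-in sits under Screening, ahead of the Randomisation section. Text order points to pre-randomisation loss.
- **That the starting settings act unchanged for 6 months.** Both arms have clinical reviews at 1 and 3 months that cover insulin requirements. The ABC4D case base is revised repeatedly: every two weeks in the text, weekly in the activities table, which must be reconciled.

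Those later reviews are open-label as well, so re-ordering Visit 2 removes one of several contacts at which the arm is known.

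**Conclusion.** The point holds for Phase 4 and, more weakly, for Phase 3. Followed in the order written, Phase 4 places a discretionary, outcome-relevant adjustment after allocation in an open-label trial, without a rule or a blinded adjuster. What is established is an avoidable opportunity for bias. Its size and direction are unknown, and the figures above rest entirely on assumed shifts. Shifts of 0.06% to 0.12% would raise type I error only to about 6% to 10% at 71 per arm, while 0.2% would bring it to about 19%. The change is worth making because it is cheap and removes one source of bias. The documents do not show that the comparison has been compromised.

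**What to change.** In Phase 4, state the Visit 2 sequence explicitly:

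1. Confirm that the run-in has been completed.
2. Carry out the CGM review.
3. Make and record any changes to ICR, ISF and basal rates.
4. Only then randomise, or disclose the allocation.
5. Start ABC4D, including initialisation of the case base, or the standard calculator.

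Use the same order in Phase 3: CGM review and recalculation of ISF and ICR first, then allocation, then the start of the assigned calculator. In both phases the settings recorded before disclosure would also let the reader check that the arms began alike.

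The cost is a re-ordering of steps within one existing visit. No visit or test is added, no dosing rule changes, and the required total stays at 142. The later reviews remain open-label, so the change reduces allocation-aware handling of insulin settings but does not end it.

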**Randomisation**

Subjects who fit the inclusion criteria will be randomized to either ABC4D (intervention group) or standard care (control group) in a 1:1 ratio

Standard care is defined as the bolus wizard within insulin pumps, bolus calculator in glucose meter or the ABC4D app as a standard bolus calculator (without CBR adaptation)

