**Subject inclusion criteria:**

- Adults ≥18 years of age
- Diagnosis of T1DM for > 1 year
- On MDI using a basal-bolus insulin regime or continuous subcutaneous insulin infusion (insulin pump)
- Structured education done
- HbA1c ≥ 48mmol/mol and ≤ 86mmol/mol
- No severe hypoglycaemia (defined as needing 3rd party assistance) in previous year

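### Phase 4 does not say which calculator each control uses and does not stratify by pump or MDI, so a difference can be credited to ABC4D as a whole system but not to CBR adaptation

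*Combined protocol and SAP*

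**What the plan says.** In Phase 4, under Randomisation, subjects are "randomized to either ABC4D (intervention group) or standard care (control group) in a 1:1 ratio", and "Both groups will be using RT-CGM". The control condition follows: "Standard care is defined as the bolus wizard within insulin pumps, bolus calculator in glucose meter or the ABC4D app", the app being used with CBR switched off. Phase 3, under its own Randomisation heading, uses the same three options ("bolus calculator in glucose meter or the ABC4D app as a standard bolus calculator (without CBR adaptation").

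The Phase 4 objective is "To demonstrate efficacy of the ABC4D with real-time CGM (RT-CGM) compared to standard care with RT-CGM". The Population paragraph describes the contrast to be powered as the fully automated ABC4D system against a standard bolus calculator. The methodology is randomised and open-label.

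On delivery mode, the Phase 4 inclusion criteria admit subjects "On MDI using a basal-bolus insulin regime or continuous subcutaneous insulin infusion (insulin pump").

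The Phase 4 control Visit 2 list includes "Adjust ICR, ISF and basal rates if deemed necessary based on CGM data" but no step that supplies, starts or trains anyone on a calculator. In Phase 3, the heading of the control Visit 2 refers to starting ABC4D, but no step beneath it does so. The Phase 4 intervention Visit 2 list includes switching on the device, a user guide, and entry of meal, exercise, alcohol, illness, stress and menstrual-cycle information.

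Neither phase gives a rule for who uses which control calculator, the expected share of each, a stratification factor, or an analysis by calculator or delivery mode.

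**The concern.** Every intervention participant moves to one smartphone app with a detailed entry routine and CBR adaptation. A control may be on a pump wizard, a meter calculator or the same app without CBR. For each control not on the app, the contrast between arms combines CBR with a change of device and entry routine. The share of such controls is not stated, so the mixture behind the result cannot be described in advance.

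Two things are at stake. The first is attribution: the novelty lies in the CBR algorithm, and readers will want to know whether it caused any HbA1c difference. The natural route is to look at people for whom the control was the non-CBR app. If the calculator is settled after an open-label allocation, nobody knows which intervention participants belong in that comparison, and choice can select the controls who do. The second is balance. Pump or MDI use bears on which control calculators are possible and on how basal insulin is delivered, yet plain 1:1 allocation leaves its balance to chance.

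**Working it through.** **1. The plan's own figure.** Inputs from the Phase 4 Population paragraph: difference 0.6% HbA1c, SD 1.1, two-sided alpha 0.05, power 90%.

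n per arm = 2 × (1.960 + 1.282)² × 1.1² / 0.6² = 70.6, rounded up to 71, or 142 in total. This matches the plan; the sample size is not in dispute here.

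The same paragraph plans 90 per arm, while the Phase 4 Statistics paragraph says 80. The two must be reconciled. The checks below run from 71 to 90 per arm to cover both.

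**2. Chance imbalance in pump share.** The documents give no pump share *p*, so 30-50% is assumed. The 95% range for the between-arm difference is ±1.96 × √[p(1−p) × 2/n].

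| n per arm | p = 30% | p = 50% |
|---|---|---|
| 71 | 1.96 × 0.0769 = 15.1 points | 1.96 × 0.0839 = 16.4 points |
| 80 | 1.96 × 0.0725 = 14.2 points | 1.96 × 0.0791 = 15.5 points |
| 90 | 1.96 × 0.0683 = 13.4 points | 1.96 × 0.0745 = 14.6 points |

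So the range is about ±13 to 16 percentage points. It cannot be turned into an HbA1c shift, because the documents give no HbA1c difference between pump and MDI users.

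**3. What the whole-arm difference contains.** Let *s* be the share of controls on the non-CBR app and *d* the HbA1c effect of moving to the app from another calculator. Leaving other differences between arms aside, the expected difference is the CBR effect + (1 − s) × d.

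Neither *s* nor *d* is in the documents, and *d* could have either sign. Purely as illustration, *d* = 0.1 to 0.3% would contribute 0.10 to 0.30 at s = 0, 0.05 to 0.15 at s = 1/2, and nothing at s = 1. The form of the expression matters more than these values: the mixing grows with the unstated share of controls off the app and vanishes if all are on it.

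**4. Power of a protected app-versus-app comparison.** If the would-be control calculator is recorded for everyone before allocation, both arms can be restricted to those for whom it is the non-CBR app. With *m* = s × n per arm, power = Φ[0.6 / (1.1 × √(2/m)) − 1.96].

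| n per arm | s = 1 | s = 1/2 | s = 1/3 |
|---|---|---|---|
| 71 | 90.1% | 63.2% | 46.7% |
| 90 | 95.5% | 73.5% | 56.1% |

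The values of *s* are assumptions. These figures keep the full 0.6% as the effect. The documents give no effect for CBR alone, and a smaller one would lower every entry.

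Setting app-using controls against the whole ABC4D arm would appear stronger (75.6% at s = 1/2 and 63.2% at s = 1/3, with 71 per arm). But it compares a selected part of one arm with all of the other, so randomisation does not protect it.

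**The case against.** The strongest reply is that isolating CBR is not the trial's question. The stated objective is ABC4D with real-time CGM against standard care with real-time CGM. Comparing a complete system with the calculators people use in practice is a legitimate pragmatic design. If pump users lose something by leaving an integrated wizard, that is a real property of the system and belongs in the result. The entry fields are also inputs to the CBR algorithm, so separating data entry from CBR is partly artificial. All of this stands, and it is why the primary comparison is not challenged.

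It is also fair that chance imbalance under valid randomisation is already allowed for in the type I error rate. Stratification here buys balance and clearer interpretation; it does not repair a bias.

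A reader might infer that the comparator is dictated by pump or MDI use. The documents do not say so: only the pump wizard requires a pump, and the choice among the remaining options is left open. A reader might also infer that app-using controls differ from ABC4D only in CBR. That is not supported either. The fields requested in non-CBR mode are not described, and the 24-hour support line, the user guide and the instruction on correction boluses appear only for the intervention group. The documents should state whether those differences are intended.

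What the reply does not answer is that even a pragmatic trial should say how its control condition is assigned. This plan enlarges recruitment so that the fully automated system can be compared separately from the semi-automatic mode used for the first 25 participants. It takes no comparable care over three different devices in the control arm.

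**Conclusion.** The concern holds in limited form. Phase 4, and Phase 3 in the same way, permits three control calculators with no assignment rule and no stratification by delivery mode. The primary comparison is sound as whole system versus standard care. It is not set up to attribute a difference to CBR adaptation, and without a calculator fixed before allocation an app-versus-app comparison would not be protected by randomisation.

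The only size that can be given is the possible chance imbalance in pump share: about ±13 to 16 percentage points (95% range) for 71 to 90 per arm, assuming 30-50% pump users.

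Two stronger readings are tempting. One is that the trial cannot separate CBR from a change of device. That is too absolute, because the mixing depends on an unstated share and is zero if every control uses the app. The other is that some definite part of the 0.6% target is a device effect. Any such figure would rest wholly on assumed values of *s* and *d*.

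**What to change.** 1. Stratify randomisation by pump versus MDI, which is known at Visit 1, and include that factor in the HbA1c model once it is specified; the Statistics paragraph names none.
2. Before allocation, record for every participant in both arms the calculator they would use as a control, and state who decides. Record actual use during follow-up.
3. Pre-specify a secondary comparison among participants whose would-be calculator is the non-CBR app, analysed by the pre-allocation record, and state that its power is lower than that of the primary analysis.
4. Word the primary conclusion as ABC4D as a whole system versus standard care.

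The cost is one stratification factor, one item on the screening form and one secondary analysis. No change in sample size is needed.

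Making the non-CBR app the only comparator is an optional trade-off, not a required change. It would leave the requirement at 142 if 0.6% and SD 1.1 are kept, and would remove the device term in step 3 of the working. But it would make the control arm less like everyday care, take control pump users off their own wizard, and still leave the support line and the correction-bolus instruction described for one arm only.
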